9.3. Patient Disposition

At the end of the study, the following categories of patients will be described:

- Number of patients who underwent Screening;
- Number of patients who were not included in the study due to non-fulfilment of eligibility criteria, and reasons for non-inclusion;
- Number of patients included (i.e. who signed the Informed Consent form, ITT patients);
- Number of patients included by stage of HAT and by treatment modality, i.e. in hospital or on an out-patient basis;
- Number of patients included who took at least one tablet of fexinidazole (mITT patients) by disease stage;
- Number of patients included, by disease stage, who completed treatment and who received all of the protocol-planned doses (treatment completers);
- Number of patients included, by disease stage, who took at least one tablet of fexinidazole, excepting those who died for reasons clearly unrelated to efficacy or safety of the IMP (evaluable patients);
- Number of patients included, by disease stage, with no major protocol violations (PP patients);
- Number of patients included, by disease stage, treated on an out-patient basis, who:
 - o temporarily interrupted treatment,
 - o prematurely discontinued treatment,
 - o were hospitalised for reasons related to non-compliance,
 - were hospitalised for a safety problem (non-exhaustive list);

Confidential Page 48 of 83

- Number of patients included, by disease stage, who underwent the following visits:
 - Screening,
 - Dispensing (Day 0), for patients treated an out-patient basis,
 - Visits during Treatment Period (Day 1 to Day 10),
 - EoT Visit.
 - o EoH Visit (Day 13 to Day 18), for patients treated in hospital,
 - o 3-month Follow-up Visit,
 - o 6-month Follow-up Visit,
 - o 12-month Follow-up Visit,
 - 18-month Follow-up Visit.
- Number of patients included, by disease stage, withdrawn from the study, categorised by reason for withdrawal.

9.4. Description of Patients at Baseline

Descriptive statistics (n, mean, standard deviation, median, minimum, maximum) or frequencies and percentages will be presented for the following patient baseline characteristics, by disease stage and overall:

- Demographic data
- Medical history
- Physical examination
- Vital signs
- Urine pregnancy test (for women of child-bearing potential)
- Laboratory tests
- Karnofsky Performance Status (separating patients treated on an out-patient basis and patients treated in hospital)
- Neurological examination
- Concomitant medication

9.5. Effectiveness Analyses

9.5.1. Primary Analysis - Effectiveness

The primary analysis will be performed on the mITT population. The success rate at 12 months and the success rate at 18 months will be estimated, bearing in mind that 18 months provides a more reliable estimate of the cure rate. The 95% exact confidence interval of the percentage will be provided.

Confidential Page 49 of 83

9.5.2. Sensitivity Analysis

The success rates at 12 and 18 months will be estimated along with the 95% exact confidence intervals on the per protocol population of patients.

9.5.3. Secondary Analysis - Effectiveness

The success rates at 12 and 18 months will be estimated in the sub-group of early-stage patients as well as the sub-group of late-stage patients. The Clopper-Pearson (exact) 95% confidence interval will be provided. The expected success rate in late-stage patients is slightly higher than that in early-stage patients, however, given the precision of the estimates, the observed rate may be lower. The proportion of early-stage patients in the study sample will also be estimated.

9.6. Secondary Analyses

9.6.1. Secondary Analysis - Safety

The secondary safety analyses will be performed on the mITT population, i.e. all patients who took at least one tablet of fexinidazole.

The proportion of patients who experienced an SAE and/or an AE leading to treatment discontinuation will be described by system-organ class using Medical Dictionary for Regulatory Affairs (MedDRA) terms and/or NCI CTCAE, version 4.03 (14) and, for certain laboratory parameters, modified CTCAE will be used (see Appendix 6 – CTCAE v4.03 adapted, p 81).

The proportion of patients who experienced at least one AE will be described. Events described using the same term and that occur several times in the same patient will be counted only once. If a patient experiences several events described with the same term, the event with the maximal severity will be included in the analysis. In addition, each SAE will be described in a narrative presenting all aspects of the medical event and the causality assessment.

The incidence of AEs and of SAEs and their respective 95% confidence intervals will be presented by category and by frequency. In other cases, only descriptive statistics will be presented.

Laboratory safety parameters, i.e. haematology and biochemistry, will also be described individually, indicating the proportions of patients by category corresponding to the size of the increase in relation to the ULN for liver function tests (< 1 ULN, 1–2 ULN, 2–3 ULN etc.). Scatter graphs with baseline values on the x-axis and post-treatment values on the y-axis with the bisector indicating the absence of change will be presented. Changes in blood levels over time will be presented in graphs. Shift tables will be provided to supplement signal detection. A listing of patients with clinically significant increases in laboratory parameters will be provided.

Confidential Page 50 of 83

Abnormalities, if any, on ECG tracings recorded on Day 11 will be described.

The proportion of patients hospitalised for a safety problem, including overdose, will also be presented.

9.6.2. Secondary Analysis - Compliance

Compliance will be assessed on the sub-group of out-patients from the ITT population, i.e. all patients who were considered as eligible for treatment on an out-patient basis and to whom the IMP was dispensed, regardless of whether or not they took the IMP.

The number and percentage of patients in whom the presence of fexinidazole or its main metabolites was detected in the blood sample collected on D11 will be presented, as well as the success rate in this sub-group of patients and in the sub-group of patients in whom no trace of fexinidazole or its main metabolites was detected. The distribution of the frequency of patients with unused tablets remaining at the end of the treatment period will be presented, and the relation between the success rate and the number of tablets remaining will be determined using a logistical regression or a sub-group analysis. The distribution of the frequencies of responses from patients during the compliance interview will be presented.

The information provided by the PK analyses, the number of tablets remaining and the questionnaire will be combined to define perfect compliance and non-compliance. Perfect compliance corresponds to a patient in whom fexinidazole is detected in the blood, who has no remaining tablets and whose report on full compliance with treatment seems unquestionable. The success rate in patients with perfect compliance will be compared to that in non-compliant patients.

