2.2.6. Secondary Endpoints - PK

The secondary endpoint for the PK assessment will be:

 PK parameters of fexinidazole and its metabolites in whole blood, measured in all patients treated in hospital.

3. Study Design

This is a prospective, multicentre, open-label study, assessing the effectiveness of fexinidazole in a cohort of adults and children with HAT at any stage, with follow-up over 18 months.

It is planned to include 174 patients in 4 investigational centres or more in the DRC and in Guinea that have experience in the treatment of patients with HAT.

Confidential Page 25 of 83

The duration of treatment is 10 days. Patients will be treated on an out-patient basis or in hospital, in accordance with pre-set inclusion and non-inclusion criteria.

The end of study corresponds to the last visit of the last patient.

4. Eligibility Criteria

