9.1. Sample Size Determination

The sample size determination is based on the primary analysis. The expected success rate is between 87% and 91% depending on the percentage of early-stage patients included in the sample. The success rate for patients with late-stage HAT should be slightly below the expected success rate of 89% in the pivotal study, DNDIHATFEX004, which has a restricted, more homogeneous population.

As concerns early-stage patients, a meta-analysis performed by Hümbelin (11), on a sample of 2524 patients treated with pentamidine and indexed in the databases of four non-governmental organisations showed a relapse rate (presence of trypanosomes or CSF WBC \geq 20/µL) of 5.63% in patients followed for 6 months or less (142/2524), 8.20% in patients followed for 12 months or less (207/2524) and 9.23% in patients followed for 18 months or less. The expected success rate for early-stage patients should be close to 92%.

A sample size of 174 patients provides a precision of \pm 5% in the estimate if the expected success rate is 87% and if a Wald confidence interval is used.

Because the confidence interval will be calculated with an exact method (Clopper-Pearson approach) the lower arm of the 95% CI will be longer than the upper arm. The precision for the lower arm will be close to 6% and that of the upper arm will be close to 4.5 % if we consider an expected success rate of 87%. The precision will be greater if the success rate is higher.

Confidential Page 47 of 83

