### 7.2. Type I error

For all analyses, the type I error ( $\alpha$ ) is set to 0.05 two-sided.

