#### Statistical modeling: logistic regression

- Model 1: the failure rate will be related to the  $\log_e$  of the number of WBC in CSF (/ $\mu$ L) at inclusion.
- Model 2: the failure rate will be related to the compliance (number of tablets left over at the end of treatment)
- Model 3: the failure rate will be related to the score equal to the sum of weighted symptoms at inclusion (5 points if sleepiness observed at entry, 4 points for prurit, 3 points for tremor, 2 points for asthenia and 1 point for headache).
- Model 4: the failure rate will be related to the presence of a symptom score of 12 or more (see model 3).

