The following analysis defined in Section 9.6.2 of the protocol will be provided by [REDACTED]: *“the number and percentage of patients in whom the presence of fexinidazole or its main metabolites was detected in the blood sample collected on D11 will be presented, as well as the success rate in this sub-group of patients and in the subgroup of patients in whom no trace of fexinidazole or its main metabolites was detected. The distribution of the frequency of the number of tablets remaining at the end of the treatment period will be presented, and the relationship between the success rate and the number of tablets remaining will be determined using a logistic regression or a sub-group analysis. The distribution of the frequencies of responses from patients during the compliance interview will be presented. The information provided by the PK analyses, the number of tablets remaining and the questionnaire will be combined to define perfect compliance and noncompliance. Perfect compliance corresponds to a patient in whom fexinidazole is detected in the blood, who has no remaining tablets and whose report on full compliance with treatment seems unquestionable. The success rate in patients with perfect compliance will be compared to that in non-compliant patients”.*

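### The logistic regressions of outcome on left-over tablets have no sparse-data method, and if left-over tablets are uncommon the slope may well have no finite estimate

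*Protocol*

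**What the plan says.** Protocol 9.6.2 plans, for out-patients in the ITT population, that "the relation between the success rate and the number of tablets remaining will be determined using a logistical regression or a sub-group analysis". SAP 8.7.3 carries this over ("will be determined using a logistic regression or a sub-group analysis") and assigns the work to a party whose name is redacted. Neither text says when the regression or the sub-group analysis applies, or which cut-points would define the sub-groups.

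SAP 8.7.2 adds, in its list of logistic models: "Model 2: the failure rate will be related to the compliance (number of tablets left over at the end of treatment"). Section 8.7.2 and the table list in SAP 9.1 place this model on all mITT patients, not on out-patients alone. It has no alternative.

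On event numbers, protocol 9.1 states that "The expected success rate is between 87% and 91% depending on the percentage of early-stage patients included in the sample", so 9-13% are expected to fail. Protocol section 3 gives the total: "It is planned to include 174 patients in 4 investigational centres or more in the DRC and in Guinea". Neither document gives the expected split between out-patients and in-patients, or the expected share with tablets left over.

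**The concern.** The covariate is zero for anyone who finishes the pack, and the outcome is fairly rare. With one such covariate, and both outcomes present among patients with no tablets left, maximum likelihood gives a finite slope only if at least one failure and at least one success have left-over tablets. If the first is missing, the slope runs to minus infinity for failure. If the second is missing, it runs to plus infinity. Software then prints whatever values it held when iteration stopped, with a huge standard error, so the Wald interval and p-value carry no information.

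At stake is one of the analyses that link out-patient intake to cure. Compliance and feasibility of self-management are secondary objectives of this trial. Under 9.6.2 and 8.7.3, a failed regression could be replaced by sub-groups chosen after the data are seen. Under Model 2 the plan offers nothing in its place.

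**Working it through.** **The plan's own figure.** The precision statement holds "if the expected success rate is 87% and if a Wald confidence interval is used". With a two-sided 5% level (SAP 7.2: "is set to 0.05 two-sided"), n = 1.96² × 0.87 × 0.13 / 0.05² = 173.8, rounded up to 174. This reproduces. It sizes the overall success rate only. The documents give no figure for the compliance regression.

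**Inputs.**
- Failure rate f: 9-13%, from protocol 9.1.
- Out-patients n: not given; assumed 60-120 of 174.
- Share r with tablets left: not given; assumed 3-10%, with 20% as a contrast.
- Association between left-over tablets and failure: none at first, then relaxed.

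**Formula.**
- A = P(no patient has both left-over tablets and a failure) = (1 − r·f)^n
- B = P(no patient has both left-over tablets and a success) = (1 − r·(1 − f))^n
- C = P(nobody has left-over tablets) = (1 − r)^n
- P(no finite slope) = A + B − C

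Cases where the patients with no tablets left lack one outcome add at most about one percentage point here.

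**Results with no association.**
- n = 80, r = 5%, f = 11%: A = 0.643, B = 0.026, C = 0.017; total 65%.
- n = 80, r = 10%, f = 11%: 41%.
- Highest (n = 60, r = 3%, f = 9%): 0.850 + 0.190 − 0.161 = 88%.
- Lowest (n = 120, r = 10%, f = 13%): 21%.
- r = 20%, n = 60-120, f = 9-13%: about 4-34%.

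**Results with an association.** Protocol 5.6.5 gives rescue treatment to out-patients who interrupt before Day 4, and the 18-month algorithm in SAP 10.1 counts rescue as failure. Some patients with left-over tablets therefore fail by rule. Suppose a quarter do and the rest fail at 11%. Their failure rate is 0.25 + 0.75 × 0.11 = 0.3325. With n = 80:
- r = 5%: 0.262 + 0.066 − 0.017 = 31%.
- r = 10%: 7%.

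If left-over tablets multiply the failure odds by four, 87 out-patients give 25-32% at r = 5% and 4-8% at r = 10%.

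**Model 2.** In-patients with no tablets left do not cure separation, because the empty cell stays empty. If all 174 patients could have left-over tablets at a 5% share with no association, the probability is still 32-46% (f = 13% to 9%).

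**Worked example.** Take 80 patients and 9 failures. Four patients have 1, 2, 3 and 6 tablets left, and all four are cured.
- Maximum likelihood diverges. One run stopped at a slope of about −15 (SE about 2,900), another at about −18 (SE about 16,000).
- Firth's method gives an odds ratio for failure of 1.06 per tablet, with a 95% profile interval of 0.17 to 1.78.
- The raw rates are 0/4 with left-over tablets and 9/76 without. The Firth point estimate thus lies on the opposite side of 1 from the raw comparison. That comes from the penalty; only the interval is informative.
- The exact upper limit for 0/4 is 1 − 0.025^(1/4) = 60%.

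**The case against.** The strongest counter-argument has five parts.

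1. *The result is not lost.* A reader might infer that the compliance analysis could return nothing usable. The documents do not support that for out-patients. The sub-group alternative gives finite rates, though imprecise ones: 0/5 failures has an exact 95% interval of 0-52%, and 0/10 of 0-31%. Protocol 9.6.2 also plans success rates by drug detected or not on Day 11, and by perfect compliance against non-compliance. SAP 8.7.2 lists tablets left over for each failure, and SAP 8.7.3 lists every patient with tablets remaining. This stands, but it does not give Model 2 a fallback.

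2. *The frequency is unknown.* A reader might infer that the regression will usually fail. The two deciding inputs are not in the documents, and the risk runs from below 1% to above 95% over wider assumptions. This stands. A low share is plausible, because protocol 4.3 selects out-patients for good understanding of dosing, but plausibility is not a figure.

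3. *No association is a doubtful assumption.* The rescue rule, and the counting of deaths and non-attendance at 18 months as failures, can put failures among patients with left-over tablets. This stands and lowers the risk as shown. It also builds part of any association in by definition.

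4. *Penalisation does not create information.* This stands. If nobody has tablets left, the slope is not identified and no estimator helps. At n = 60 and r = 3%, that case alone has probability 0.97^60 = 16%.

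5. *The detail may be elsewhere.* The SAP 8.7.3 analysis belongs to another party, who may hold a fuller specification. That is possible, but Model 2 stands in this SAP without one.

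**Conclusion.** The point holds as a gap in a secondary analysis. SAP Model 2, and the regression option in protocol 9.6.2 and SAP 8.7.3, have no sparse-data method, and there is no rule for moving between regression and sub-groups.

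The chance of no finite slope is material if left-over tablets are uncommon: about 21-88% under the stated assumptions with no association. It is modest or small if they are common or clearly linked to failure. These figures rest on an assumed number of out-patients and an assumed left-over share, so they show a range of risk and do not forecast this trial.

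The primary success rate and its interval are unaffected. Because the repair costs so little, it should be made, but it does not bear on the trial's main conclusion.

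**What to change.** In SAP 8.7.2 (Model 2), SAP 8.7.3 and protocol 9.6.2:

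- Fit the regression by Firth penalised likelihood, with profile penalised-likelihood 95% intervals (the FIRTH option in SAS PROC LOGISTIC) and exact logistic regression as a check.
- Always show beside it the failures among patients with and without left-over tablets, with Clopper-Pearson intervals. Make this sub-group table a pre-specified companion to the model, replacing the present either/or choice.
- State that, if no patient with left-over tablets fails, the interval is interpreted and the Firth point estimate is not.
- State that no model is fitted if nobody has tablets left over.

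The cost is a few SAP sentences and one option in the software already specified in SAP 7.1. No new data are needed. The downsides are a slightly less familiar method and a point estimate shaped by the penalty when the data are very sparse, which is why the raw table must stay beside it.

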## 6. ENDPOINTS

### 6.1. Primary endpoint

The primary endpoint for the assessment of effectiveness will be the outcome (success or failure) at 18 months after the end of treatment. Success is defined as a cure, according to the criteria adapted from the WHO.

The outcome (success or failure) at 18 months will be calculated using the algorithm defined in [Section 10.1](#).

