#### 6.2.2. Compliance

As defined in the protocol, the secondary endpoints for the assessment of compliance with treatment in patients treated on an outpatient basis will be:

- Presence of fexinidazole and/or its main metabolites in the blood sample collected on Day 11 and/or at any unscheduled visit between Day 1 and the end-of-treatment (EoT) visit (*note: this endpoint will be analyzed by [REDACTED]*)
- Patients who had tablets left over at the end of treatment (i.e. number of tablets returned on day 11 > 0) (yes/no)
- Number of tablets left over at the end of treatment (i.e. number of tablets returned on day 11) (0, 1, 2, ...)
- Patients' responses to the questionnaire at the compliance interview on Day 11: Questions 5, 5.1, 5.2, 5.3 and 5.4.

In addition, the following endpoints will be assessed on all patients (i.e. inpatients and outpatients):

- Patients who completed the full course of treatment (i.e. at least 10 days) (yes/no)
- Patients fully compliant (i.e. children with body weight less than 35 kg who took exactly 14 tablets or children with body weight who took exactly 24 tablets or adults who took exactly 24 tablets) (yes/no)
- Patients who always took their treatment during a meal (yes/no)
- Patients who had at least one re-administration (yes/no)

- Patients who had at least one re-administration due to vomiting (yes/no)
- Patients who had at least one re-administration due to other reason (yes/no)
- Number of re-administration(s) by patient (0, 1, 2, ...)
- Overall compliance defined as:

- For patients with body weight < 35 kg (Children):

$$\text{Compliance (\%)} = \frac{100 \times \text{Actual dose taken (mg)}}{8400 \text{ mg (i.e. } 1200 \text{ mg} \times 4 \text{ days} + 600 \text{ mg} \times 6 \text{ days)}}$$

- For patients with body weight ≥ 35 kg (Children) or Adults:

$$\text{Compliance (\%)} = \frac{100 \times \text{Actual dose taken (mg)}}{14400 \text{ mg (i.e. } 1800 \text{ mg} \times 4 \text{ days} + 1200 \text{ mg} \times 6 \text{ days)}}$$

Note for overall compliance:

*Actual dose taken (mg) = 600 mg X number of tablets taken*

*Number of tablets taken = (sum of tablets taken from Day 1 to Day 11) + (sum of tablets taken for re-administration from D1 to D11)*

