### 6.2.3. Feasibility

As defined in the protocol, the secondary endpoints for assessment of the feasibility of self-management of treatment intake, or with the assistance of the caregiver under recommended conditions are the following for patients treated on an outpatient basis:

- Patients who temporarily discontinued their treatment (yes/no)
- Patients who prematurely (i.e. prior to Day 10) discontinued their treatment (permanent interruption) (yes/no)
- Patients who delayed starting treatment (i.e. date of D1 – date of D0 > 1 day) (yes/no)
- Patients who mislaid treatment units (i.e. number of tablets left over > 0) (yes/no)
- Patients who were hospitalized during their treatment period
- Patients with:
  - 1, 2, 3, ..., 9, 10 days of treatment administration performed at the hospital.
  - 0 days (=treatment administration performed at home only).
- Patients who took treatment regularly, according to the patients themselves (=questionnaire on Day 11: Question 5 “How did you take your treatment?”) (yes/no)
- Patients who understood the instructions concerning the dosing regimen of fexinidazole (=questionnaire on Day 0: patients who correctly answered to the 8 questions) (yes/no)
- Patients who complied with the dosing regimen, including intake of treatment during a meal (=questionnaire on Day 11: patients who correctly answered to the 4 questions 5.1 to 5.4) (yes/no)

In addition, the following data will be listed:

- Reasons of temporary treatment discontinuation
- Reasons of premature and permanent treatment discontinuation
- Reasons of hospitalization during the treatment period

The following data will also be described in patients treated in hospital:

- Patients who temporarily discontinued their treatment (yes/no)

- Patients who prematurely discontinued their treatment (permanent interruption) (yes/no)

The following data will also be listed in patients treated in hospital:

- Reasons of temporary treatment discontinuation
- Reasons of premature and permanent treatment discontinuation

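### Perfect compliance rests partly on an opinion about the patient's report that has no rule and need not be formed blind to outcome, which leaves one secondary success-rate comparison open to outcome-dependent sorting

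*Protocol*

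**What the plan says.** Protocol 9.6.2 sets the population: "Compliance will be assessed on the sub-group of out-patients from the ITT population". Three sources are brought together: blood results, tablet count and interview. In its words, "the number of tablets remaining and the questionnaire will be combined to define perfect compliance and non-compliance". Only the first class is then spelled out. A perfect complier has drug in the blood and is someone "who has no remaining tablets and whose report on full compliance with treatment seems unquestionable". No separate definition of non-compliance follows.

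SAP 8.7.3 reproduces this text, including "whose report on full compliance with treatment seems unquestionable", adds no rule, and assigns the analysis to a party whose name is redacted. It ends with the comparison: "The success rate in patients with perfect compliance will be compared to that in non-compliant patients". No test is named.

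On timing, SAP 6.2.2 lists "Patients' responses to the questionnaire at the compliance interview on Day 11: Questions 5, 5.1, 5.2, 5.3 and 5.4", while SAP 6.1 sets the primary outcome as "the outcome (success or failure) at 18 months after the end of treatment".

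For a different purpose, SAP 6.2.3 already turns the same interview into yes/no variables. One is Question 5, on regular intake. The other counts "patients who correctly answered to the 4 questions 5.1 to 5.4". Neither is tied to perfect compliance.

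**The concern.** Two of the three criteria are recorded facts. The third depends on how convincing someone finds the patient's account. The Day 11 answers themselves cannot be influenced by a relapse a year later, but their interpretation can be if it happens once outcomes are known. Someone who knows that a patient relapsed has a natural reason to doubt a claim of full intake, and less reason to doubt the same claim from a cured patient.

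If that happens, failures drift into the non-compliant group. Success under perfect compliance then looks better than it is, and compliance appears linked to cure even when it is not. Self-managed out-patient treatment is a central aim of this study, and this comparison invites the reading that relapses came from poor intake rather than from the drug.

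**Working it through.** **The plan's own figures.** The documents give no figure for this comparison. The nearest design figure is the sample size, and it reproduces: n = 1.96² × 0.87 × 0.13 / 0.05² = 173.8, rounded up to 174. It says nothing about how many patients will be out-patients or how many reports will be doubtful, so the size of the bias can only be shown under assumptions.

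**Main illustration, with no true compliance effect**

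Assumed inputs (none is in the documents):
- 80 out-patients with 87.5% success, so 70 successes and 10 failures. The protocol expects 87% to 91% overall.
- 10% non-compliant on tablets or blood level, unrelated to outcome: 7 successes and 1 failure. This leaves 63 successes and 9 failures whose class depends on the report.
- Reports doubted in a fraction a = 0.05 of those successes and a fraction b of those failures.

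Formulas:
- Success with perfect compliance = 63(1 − a) / [63(1 − a) + 9(1 − b)]
- Success without = (7 + 63a) / [(7 + 63a) + (1 + 9b)]

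With a = 0.05, there are 59.85 successes in the perfect group and 10.15 in the other.

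| b | Perfect | Non-compliant | Gap (points) |
|---|---|---|---|
| 0.05 | 59.85/68.40 = 87.5% | 10.15/11.60 = 87.5% | 0 |
| 0.10 | 59.85/67.95 = 88.1% | 10.15/12.05 = 84.2% | 4 |
| 0.20 | 59.85/67.05 = 89.3% | 10.15/12.95 = 78.4% | 11 |
| 0.30 | 59.85/66.15 = 90.5% | 10.15/13.85 = 73.3% | 17 |

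The number moved by opinion is small: 3.15 + 9b, or about 4 to 6 patients for b from 0.10 to 0.30.

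**Wider range.** A second calculation assumed 50, 87 or 130 out-patients, 87% or 91% success, 10% objectively non-compliant and a further 10% to 30% with a report open to judgement. Two-sided Fisher tests at 0.05 were simulated 4,000 times per scenario. Results for 87 out-patients, 87% success and 20% borderline reports:

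| Borderline reports doubted: successes / failures | Spurious gap (points) | False-positive rate |
|---|---|---|
| 30% / 60% | 4.9 | 6.4% |
| 20% / 80% | 10.3 | 16% |
| 0% / 100% | 20.5 | 40% |

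Over all outcome-dependent scenarios the gap ran from 2 to 28 points and the false-positive rate from 3% to 80%. The upper ends need extreme outcome dependence together with many borderline reports. With doubt at 30% in successes and failures alike, the expected gap was 0 and the false-positive rate 1.4% to 3.5%.

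**The case against.** The strongest reply is that outcome-dependent judging is inferred. The interview takes place at the end of treatment, and the documents do not say who judges the report or when. Running the comparison after follow-up does not date the classification. This stands: a reader might infer that patients are sorted with the outcome in view, but the documents are silent on this. What can be said is that nothing in them prevents it.

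A reader might also blame the open-label design. That is not the mechanism. What matters is whether the classifier is masked to outcome, and this could be arranged in a single-arm open study.

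A larger effect is tempting too. If every out-patient is taken as compliant on tablets and blood level, the same doubt rates give gaps of 10, 26 and 37 points. The protocol builds the class from those two sources as well, so this leaves out patients who are non-compliant on recorded facts. Adding 10% of them cuts the gaps to about 4, 11 and 17.

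The rule may exist elsewhere. The analysis belongs to a redacted party, the SAP places PK work in a separate plan, and SAP 8.2 mentions a data review plan. This is possible, but SAP 8.7.3 presents the wording as the definition and points to no rule for this criterion.

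Finally, the reach is limited. The primary analysis (SAP 8.6) counts every failure whatever the compliance. Model 2 (SAP 8.7.2) uses left-over tablets, and the drug-detected subgroup in Protocol 9.6.2 uses the assay. None relies on the opinion. This stands, and it confines the point to one secondary comparison.

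**Conclusion.** The point holds in this limited form. One of the three criteria for perfect compliance is an opinion with no rule, assessor, date or masking, and the resulting groups are compared on success. The comparison is exposed to outcome-dependent sorting. Whether that occurs cannot be told from the documents.

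The main illustration gives about 4 to 17 points and rests wholly on its assumed inputs. The bias is small if few reports are doubtful or doubt depends only weakly on outcome, and zero in expectation if doubt is independent of outcome. A reader might go further and conclude that the effectiveness results are compromised. They are not, because no effectiveness estimate uses this classification. The change is worth making because rule-based interview variables already exist in the SAP.

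**What to change.** Make the change in SAP 8.7.3 and record it in SAP Section 11 as a departure from Protocol 9.6.2.

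- **Rule.** Derive perfect compliance by program from three conditions: Question 5 answered as regular intake and Questions 5.1 to 5.4 all answered correctly, as in SAP 6.2.3; no tablets remaining; drug detected in the end-of-treatment sample. State whether metabolites count as detection, since Protocol 9.6.2 includes them for the detected subgroup but names only fexinidazole for perfect compliance.
- **Data cut.** Use data up to the end-of-treatment visit: Day 11, or Day 12 when the one-day delay in Protocol 8.1 applies. A strict Day 11 cut would drop patients whom SAP 6.2.2 counts as completers.
- **No manual reclassification.**
- **Other group.** Define non-compliant as every out-patient who does not meet all three conditions, or show those who meet only some as a separate group.
- **Label.** Call the comparison descriptive. A rule does not make it causal: under Protocol 5.6.5 an out-patient who interrupts before Day 4 receives rescue treatment, and SAP Section 10 counts rescue as failure.

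The data are already collected, so the cost is a short SAP amendment and some programming. SAP Section 11 already lists a change made after database lock, so this one should be dated and its timing stated. Using a rule already in the SAP limits the scope for an outcome-driven choice. Two things are given up. Some clinical nuance on doubtful reports is lost, and because the SAP 6.2.3 item includes intake with a meal, the class becomes slightly stricter than tablet compliance alone. The SAP should also state which answers to 5.1 to 5.4 count as correct, because the two documents do not show this.
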